### ***12.7.6.2 Physical Assessment - Knee***

All knee physical assessment findings will be listed and/or summarized.

## 13. SAFETY AND ADVERSE EVENTS

### 13.1 Definitions

#### 13.1.1 Adverse Event

An AE can be any unfavorable and unintended sign, symptom, or disease temporally associated with the use of a study device, whether or not considered related to the study device.

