## **11. STUDY PROCEDURES**

### **11.1 Study Interventions**

#### **11.1.1 Single Medial Femoral Chondral Lesion Treatment plus Partial Medial Meniscectomy Procedure**

A diagnostic arthroscopic evaluation will be conducted to confirm the area of treatment. If all arthroscopic eligibility criteria are met, the subject will be randomized to one of the following two treatments:

- Radiofrequency-Based Debridement (study devices)
- Mechanical Debridement (control device)

If randomized to Radiofrequency-Based Debridement, the subject will receive the Quantum 2 Controller plus Paragon T2 ICW Wand or the WEREWOLF Controller plus FLOW 50 Wand.

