**Figure 12-1: Sample Size and Statistical Power Calculation**

### 12.4 Randomization

This is a multi-center, randomized clinical study. The randomization will be by-site randomization to assure balanced number of subjects between the study devices and control device group in each investigational site.

The randomization will be in 1:1 ratio (i.e., study devices: control device). In each investigational site, subjects who are eligible for randomization will be randomized in a double-blind manner to a device.

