### **13.2 Recording of Adverse Events**

At each contact with the subject, the Investigator must seek information on AEs through questioning. Information on all AEs should be recorded immediately in the source document and in the appropriate AE module of the CRF. All clearly related signs, symptoms, and abnormal diagnostic procedures results should be recorded in the source document, though should be grouped under one diagnosis.

All AEs occurring during the study must be recorded in standard medical terminology. The clinical course of each event should be followed until resolution, stabilization, or until it has been determined that the study intervention or participation is not the cause. All unresolved AEs should be followed by the Investigator until the events are resolved, the subject is lost to follow-up, through the end of the study, or until it has been determined that the study intervention or participation is not the cause (whichever timing occurs first). Any Serious Adverse Event (SAE) that occurs until thirty (30) days after the study and is considered to be related to the study device or study participation should be recorded and reported immediately.

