#### 13.3.2 Reporting Adverse Events

Any AE (clinical sign, symptom, or disease) temporally associated with the use of this study device, whether or not considered related to the study device, shall be documented on the AE CRF, except those physical assessment findings that are considered to be clinically insignificant. All AEs meeting the above noted criteria reported by the subject or observed by the Investigator will be individually listed. The description of the event (confirmed diagnosis, if available), date of onset, date of resolution, severity and relationship to study device, action taken, outcome, and seriousness will be reported.

The Investigator will evaluate all AEs as follows:

- ***CTCAE Grade (Intensity) Assessment***

The guidelines outlined in CTCAE v4.03 will be used for assessing the intensity of the event. The general guidelines for assessing the AE grade appear below. Full guidelines may be obtained at <http://evs.nci.nih.gov/ftp1/CTCAE>.

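### The AE definition, the AE CRF rule and the relatedness categories name only the study (radiofrequency) device, although the protocol plans AE collection and summaries in both arms

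*Protocol*

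**What the plan says.** The protocol keeps two device terms apart. Section 11.1.1 lists the randomized options as "Radiofrequency-Based Debridement (study devices") and "Mechanical Debridement (control device"). Section 12.4 uses the same pair, stating that randomization by site is meant "to assure balanced number of subjects between the study devices and control device group in each investigational site".

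The adverse event rules use only the first term. Section 13.1.1 covers an unfavorable sign, symptom or disease "temporally associated with the use of a study device", related to it or not. Section 13.3.2 requires that any AE "temporally associated with the use of this study device, whether or not considered related to the study device, shall be documented on the AE CRF", and then says that AEs meeting those criteria will be individually listed. The Related and Not Related categories in the same section turn on the time sequence from administration of the study device. Section 12.7.6.1 plans a table of treatment-emergent AEs by relationship to the study device.

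Other text has no device condition. Section 13.2 says "All AEs occurring during the study must be recorded in standard medical terminology" and sends information on all AEs to the AE module of the CRF. Section 12.7.6.1 also summarizes treatment-emergent AEs by treatment group.

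**The concern.** Adverse events are the only safety assessment listed in the synopsis and in Section 12.2.3, and they are to be shown by arm. That display is informative only if an event is recognized, recorded and attributed by the same rule whichever device was used. Here the rules that decide what counts as an AE, what goes on the AE CRF and what counts as related are written around one arm's device.

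The people applying them are not masked. Investigators perform the procedure, so they know the device, and Section 12.5 describes blinding only for subjects and for the radiologists. Section 13.3.2 makes the investigator responsible for causality. An event that is never entered, or is entered with the wrong relationship, cannot be put right at the analysis stage.

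**Working it through.** The protocol states no figure to reproduce. The check is textual, with one proportion.

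**1. What the term means.** The synopsis and Sections 6, 11.1.1, 12.1 and 12.4 all use 'study devices' for radiofrequency and 'control device' for mechanical debridement. Section 12.3 counts 41 subjects in the study device group and 41 in the control device group. The safety chapter keeps that meaning: Section 13.8.2, on study device risks, lists burns and inadvertent ablation, and Section 13.8.3, on study device benefits, lists features of the radiofrequency wands.

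**2. Who lacks an anchor on a literal reading.** Control group / all randomized = 41/82 = 50%.

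**3. The provisions side by side.**

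| Provision | Anchor | Reaches a control-arm event as written? |
|---|---|---|
| AE definition, 13.1.1 | study device | No |
| AE CRF rule and listing, 13.3.2 | study device | No |
| Related / Not Related, 13.3.2 | study device | Cannot be Related |
| Relatedness table, 12.7.6.1 | study device | Relationship to the other arm's device only |
| Adverse device effect, 13.1.2 | the device, unspecified | Unclear |
| Lead-in to causality, 13.3.2 | study device/treatment | Yes |
| AE recording, 13.2 | none stated | Yes, if AE is read broadly |
| Reporting period, 13.3.1 | any study treatment or randomization | Yes |
| Treatment-emergent AE, 12.7.6.1 | first randomized treatment | Yes |
| Safety population, 12.6.3 | device/treatment received | Yes |
| Hospitalization as an SAE, 13.3.3 | after randomization | Yes |
| Visit schedule, Table 3 | surgery and every follow-up visit | Yes |

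**4. Does Section 13.2 close the gap?** Not fully. It requires all AEs to be recorded, but an AE is what Section 13.1.1 says it is. The duty is broad; the defined term under it is narrow.

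**5. The relatedness categories applied to a control-arm event.** Suppose the mechanical shaver causes the event.
- Related needs a reasonable time sequence from the study device and a known response pattern to the suspected device. The subject received no study device, so the first condition fails.
- Not Related needs no such time sequence and a likely origin in the subject's clinical state or in other therapy given. Both conditions can be met, since the shaver counts as other therapy.

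The event is therefore Not Related by wording, although its own device caused it. A device-caused event in the radiofrequency arm can be Related. Taken literally, the control column of the relatedness table would show no related events, whatever was observed.

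**The case against.** The strongest reply is that the protocol plainly means to collect AEs in both arms and that 'study device' in Section 13 is loose template wording. Section 13.2 requires questioning at every contact. The reporting period, the treatment-emergent definition, the Safety population, the hospitalization rule and the visit table all operate without regard to arm. By-group summaries would be pointless if one group could have no AEs. Section 13.3.2 itself opens the causality text with the broader study device/treatment and then shortens it, which suggests that the short form stands for the long one. Section 12.7.6.1 also refers to the worst relationship to the intervention.

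Most of this stands. A reader might infer that control-arm events reach the CRF only when tied to radiofrequency, that the control arm would therefore show no AEs, and that the safety comparison is unequal. The documents do not support that. Neither Section 13.1.1 nor Section 13.3.2 contains an exclusion or the word 'only', and the provisions just listed require collection in both arms. A percentage-point bias is equally unsupported: any such figure would be an assumed event rate multiplied by an assumed degree of under-recording.

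Two things survive. The intended reading has to be assembled from other sections, while the definition and the CRF rule that sites use day to day name one device. And loose drafting does not give a control-arm event a usable Related category, because the category definitions and the planned table both specify the study device.

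**Conclusion.** The point holds as an internal contradiction that should be corrected. The protocol plans AE collection and summaries in both arms, but four provisions that feed those summaries are anchored on the radiofrequency device alone. The contradiction is clearest for relatedness, where the literal rule admits no related event in the control group. For recording in general it is a risk of uneven practice, not a demonstrated imbalance.

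Its reach is the 41 control subjects, half of those randomized; its numerical effect cannot be derived from the documents. Safety is tabulated without hypothesis testing (Sections 12.7 and 12.7.6), so no error rate is involved, and the KOOS primary endpoint, power and alpha are untouched. Section 12.7.6.2 also places knee physical assessment findings within the safety analyses, so AE tables are not quite the whole safety display.

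The practical risk assumes that some sites apply the wording as written, that the CRF relationship item follows Section 13.3.2 (the CRF is not shown), and that the person judging causality knows which device was used.

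**What to change.** In Sections 13.1.1, 13.1.2, 13.3.2 (the AE CRF rule and the Related and Not Related categories) and 12.7.6.1 (the relatedness table), replace the study device as anchor with the assigned study treatment (study or control device) or the index procedure. Record relationship as two separate items, to the device used and to the procedure, with the same categories in both arms, and tabulate both by treatment group.

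The cost is a wording amendment and a CRF label change. Design, sample size and visit schedule stay as they are. If subjects have already been treated, ask sites to confirm that control-arm AEs were entered, and to reassess the relationship of existing entries under the common wording.

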#### 13.1.2 Adverse Device Effect

ADEs are AEs caused by or related to the device.

#### 13.1.3 Serious Adverse Events

Events are classified as serious if they meet any of the following criteria (in accordance with the recommendations of ICH [Federal Register, October 7, 1997, Vol. 62, No. 194, pp 52239-45]):

- Results in death,
- Is life-threatening (NOTE: the term “life-threatening” in the definition of “serious” refers to an event in which the subject was at risk of death at the time of the event; it does not refer to an event which hypothetically might have caused death if it were more severe),
- Requires inpatient hospitalization or prolongation of existing hospitalization,
- Results in persistent or significant disability/incapacity,
- Is a congenital anomaly/birth defect

Additionally, events are classified as serious if they meet any of the following criteria:

- Requires intervention to prevent permanent impairment/damage, or
- Important medical events that may not result in death, be life-threatening, or require hospitalization may be considered a serious adverse device effect when, based upon appropriate medical judgment, they may jeopardize the subject and may require medical or surgical intervention to prevent one of the outcomes listed above.

#### **13.1.4 Unanticipated Adverse Device Effect**

An Unanticipated Adverse Device Effect is described as any serious adverse effect on health or safety or any life-threatening problem or death caused by or associated with a device, if that effect, problem, or death was not previously identified in nature, severity, or degree of incidence in the investigational plan or application (including a supplementary plan or application), or any other unanticipated serious problem associated with a device that relates to the rights, safety, or welfare of subjects (21 CFR 812.3(s)).

### **13.2 Recording of Adverse Events**

At each contact with the subject, the Investigator must seek information on AEs through questioning. Information on all AEs should be recorded immediately in the source document and in the appropriate AE module of the CRF. All clearly related signs, symptoms, and abnormal diagnostic procedures results should be recorded in the source document, though should be grouped under one diagnosis.

All AEs occurring during the study must be recorded in standard medical terminology. The clinical course of each event should be followed until resolution, stabilization, or until it has been determined that the study intervention or participation is not the cause. All unresolved AEs should be followed by the Investigator until the events are resolved, the subject is lost to follow-up, through the end of the study, or until it has been determined that the study intervention or participation is not the cause (whichever timing occurs first). Any Serious Adverse Event (SAE) that occurs until thirty (30) days after the study and is considered to be related to the study device or study participation should be recorded and reported immediately.

### 13.3 Reporting

#### 13.3.1 Adverse Event Reporting Period

The study period during which AEs must be reported is defined as from the initiation of any study treatment or randomization through the end of the study intervention follow-up.

#### 13.3.2 Reporting Adverse Events

Any AE (clinical sign, symptom, or disease) temporally associated with the use of this study device, whether or not considered related to the study device, shall be documented on the AE CRF, except those physical assessment findings that are considered to be clinically insignificant. All AEs meeting the above noted criteria reported by the subject or observed by the Investigator will be individually listed. The description of the event (confirmed diagnosis, if available), date of onset, date of resolution, severity and relationship to study device, action taken, outcome, and seriousness will be reported.

The Investigator will evaluate all AEs as follows:

- ***CTCAE Grade (Intensity) Assessment***

The guidelines outlined in CTCAE v4.03 will be used for assessing the intensity of the event. The general guidelines for assessing the AE grade appear below. Full guidelines may be obtained at <http://evs.nci.nih.gov/ftp1/CTCAE>.

The outcome of the event will be assessed as either: resolved, resolved with sequelae, ongoing, lost to follow-up or death. Only one AE per subject is allowed to have an outcome assessment as “death.” If there are multiple causes of death for a given subject, only the primary cause of death will have an outcome of death.

### **13.3.3 Reporting Serious Adverse Events and Incidents**

For any SAE, the Principal Investigator must submit a completed AE CRF via email to the Sponsor’s Medical Monitor, within 24 hours of becoming aware of the event and send the completed Serious Adverse Event/Unanticipated Adverse Device Effect (SAE/UADE) Report via email to the Sponsor’s Medical Monitor within 48 hours. In addition, all IRB/REB reporting requirements will be followed.

The Principal Investigator shall make an accurate and adequate report of any **SAEs or Unanticipated Adverse Device Effects (UADE)**. The Principal Investigator shall document any such report on the appropriate CRF and email any initial or follow-up report to the Sponsor’s Medical Monitor and to the IRB/REB (as applicable) that has reviewed and continues to review the study.

- **Pre-existing Condition:**

A pre-existing condition, other than the condition being treated, is one that is present at the start of the study. A preexisting condition should be recorded as an AE if the frequency, intensity, or the character of the condition worsens during the study.

- **General Physical Assessment Findings:**

At screening, any clinically significant abnormality should be recorded as a preexisting condition. At the end of the study, any new clinically significant findings/abnormalities that meet the definition of a SAE must be recorded and documented as a SAE.

- **Post-study Serious Adverse Event:**

All unresolved SAEs should be followed by the Investigator until the events are resolved, the subject is lost to follow-up, through the end of the study, or until it has been determined that the study intervention or participation is not the cause (whichever timing occurs first). At the last scheduled visit, the Investigator should instruct each subject to report any subsequent event(s) until thirty (30) days after study completion that the subject or the subject's personal physician believes to be related to participation in the study. The Investigator should notify the Sponsor's Medical Monitor of any death or SAE occurring at any time after a subject has discontinued or terminated study participation that is related to the study.

- **Hospitalization, Prolonged Hospitalization, or Surgery:**

Any medical conditions that occurs after randomization and results in hospitalization or prolonged hospitalization should be documented and reported as a SAE unless specifically instructed otherwise in this protocol. Any condition responsible for surgery should be documented as a SAE if the condition meets the criteria for a SAE.

Neither the condition, hospitalization, prolonged hospitalization, nor surgery are reported as a SAE in the following circumstances:

- Hospitalization or prolonged hospitalization for diagnostic or elective surgical procedures for a preexisting condition.
- Hospitalization or prolonged hospitalization for therapy of the target disease of the study, unless it is a worsening or increase in frequency of hospital admissions as judged by the Investigator (e.g., secondary post-operative hemorrhage).

#### ***13.3.3.1 Investigator Reporting: Notifying the Sponsor***

Any SAE or UADE must be reported to the Sponsor's Medical Monitor by submitting a completed AE CRF via email within 24 hours of becoming aware of the event:

### ***13.3.3.2 Investigator Reporting: Notifying the IRB/REB***

Investigators are responsible for safety reporting to their IRB/REB. Investigators are responsible for complying with their IRB/REB's reporting requirements for SAEs, though they must notify their IRB/REB within 10 working days of becoming aware of the event for any potential UADEs (21 CFR 812.150(a)(1)). The Sponsor or its designee will provide safety reports to the Investigators to assist with reporting to the IRB/REB's. Copies of each safety report and documentation of IRB/REB notification and receipt will be kept in the Trial Master File/Study Master File.

### ***13.3.3.3 Reporting Deaths***

The following describes the Investigator reporting requirements in the event of a death, considered a SAE, which occurs during the course of a study:

- Notify the Sponsor's Medical Monitor by submitting a completed AE CRF via email within 24 hours of becoming aware of the event,
- Provide the completed SAE/UADE Report Form via email to the Sponsor's Medical Monitor within 48 hours of the event,
- Notify the IRB/REB of the death per IRB/REB reporting requirements.

Should the Investigator determine the death to be device-related and unanticipated, it is considered an UADE, and the following Investigator reporting requirements should be followed:

- Notify the Sponsor's Medical Monitor by submitting a completed AE CRF via email within 24 hours of becoming aware of the event,
- Provide the completed SAE/UADE Report Form via email to the Sponsor's Medical Monitor within 48 hours of the event,
- Notify the IRB/REB of the death per IRB/REB reporting requirements, but no later than 10 days of becoming aware of the event.

#### **13.3.4 Informed Consent Violation Reporting**

If the Investigator uses the study device without obtaining informed consent, the Investigator shall report such use to the Sponsor and the reviewing IRB/REB within 5 working days after the use occurs (21 CFR 812.150(a)(5)).

#### **13.3.5 Protocol Deviation Reporting**

The Investigator shall notify the Sponsor and the reviewing IRB/REB of any deviation from the protocol to protect the life or physical well-being of a subject in an emergency. Such notice shall be given as soon as possible, but in no event later than 5 working days after the emergency occurred (21 CFR 812.150(a)(4)). All other deviations from the protocol will be reported on the appropriate CRF and reported to the IRB/REB, if required. Every effort shall be made to comply with the requirements of the protocol to avoid deviations.

#### **13.3.6 Progress Reports**

The Investigator shall submit Progress Reports on the study to the Sponsor and the reviewing IRB/REB at regular intervals, but in no event less often than yearly (21 CFR 812.150(a)(3)).

#### **13.3.7 Final Report**

The Investigator shall, within 3 months after termination or completion of the study or the Investigator's part of the study, submit a Final Report to the Sponsor and the reviewing IRB/REB (21 CFR 812.150(a)(6)).

### **13.4 Unblinding Procedures**

Data are to remain blinded per protocol throughout the study. However, unblinding of subjects will occur by the DSMB, data manager and/or statisticians in the event of a SAE that is deemed related to the study intervention. If time permits, the Investigator should make every attempt to contact the Sponsor and/or trial Medical Monitor before unblinding any

subjects' device/treatment. For emergent unblinding, appropriate study personnel must contact the Sponsor and the Medical Monitor as soon as possible after the incident to report the details surrounding the emergency unblind and to receive instruction on follow-up procedures.

### **13.5 Data Safety Monitoring Board**

The Data and Safety Monitoring Board (DSMB) consists of a group of individuals, appointed by the Sponsor or its designee, with pertinent expertise that will review accumulated data at the interim analysis from the study. The DSMB advises the Sponsor regarding the continuing safety of subjects and those yet to be voluntarily recruited to the study, as well as the continuing validity and scientific merit of the study. Unblinded data reviewed by the DSMB will be kept confidential and protected from inadvertent or inappropriate access by the Sponsor or its designee. Following review of data generated from the interim analysis, the DSMB may advise the Sponsor to continue, redesign, or stop the study.

